Cover Page for NCT02370251

Compassionate Use of Omegaven in Children

PI: [name]

February 19, 2018

COMPASSIONATE USE PROTOCOL
Compassionate Use of Omegaven for the Treatment of
Parenteral-Nutrition-Associated Liver Disease in Children
(IRB 5451)

Principal Investigator: [name], MSMI; Pediatrics, Neonatology
Sub-Investigators: [name]; Pediatrics, Gastroenterology
Safety Monitor: [name], MS, APRN; Clinical Nurse Specialist
Inpatient Study Nurses: [name]; Neonatology
 [name]; Neonatology
Outpatient Study Nurse: [name]; Gastroenterology
Data Manager: [name]; Neonatology
Regulatory Research: [name], APRN; Neonatology

Abstract

This is a single-group assignment, open-label protocol for the compassionate use of Omegaven® 10% in 200 children less than 6 years of age who are diagnosed with parenteral-nutrition-associated liver disease and have failed conventional lipid reduction strategies. The primary objective is to safely provide Omegaven (fish oil lipid emulsion) to Oklahoma children who are dependent on parenteral nutrition and to determine the number of these children who have resolution of their cholestasis while on the emulsion. Omegaven at the FDA maximum dose of 1 g/kg/day will be used with informed consent after the failure of conventional therapies to prevent the progression of liver disease. Children will be eligible if they are dependent on parenteral nutrition and have a direct bilirubin level of ≥ 2 mg/dL on two consecutive tests at least 48 hours apart while on an average of < 2 g/kg/day of parenteral lipids or ≥ 5 mg/dL on an average of 1 g/kg/day for 7 days prior. Lab studies will be obtained to monitor safety and efficacy. Children will remain on Omegaven until their physician or guardian decides to no longer utilize the lipid emulsion. Safety outcomes and the resolution of cholestasis will be monitored and reported to the FDA and IRB.

Background and Significance

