One conventional therapy to prevent or treat cholestasis is lipid minimization, such that the IV lipid dose is reduced to levels below recommended intake amounts, compounding the growth failure inherent in infants with gastrointestinal disorders. In those receiving Omegaven, their dose is limited by regulations to 1 g/kg/day, also below the recommended lipid intake. Since fats have the highest caloric density of nutrients, maximizing intake is an important aspect of providing nutritional support. The combination of maximum Omegaven dosing supplemented with lower doses of Intralipid could theoretically provide a more balanced intake of essential fatty acids as well as improved growth in this vulnerable population.

Infants in our institution with severe PNALD were transferred outside of Oklahoma to centers approved to provide Omegave through “compassionate use” protocols as it is not available in the U.S. for routine use. In 2014, The Children’s Hospital had approximately 130 inpatient and 30 outpatient children between birth and 18 years of age with direct bilirubin levels above 4 mg/dL.¹⁰ Liver failure leads to approximately five liver transplants annually in Oklahoma children. While not all of these are due to parenteral nutrition, the ability to prevent even one transplant yearly would result in a massive savings of healthcare dollars as well as improved quality of life for those affected.

This protocol will help delineate the safety and efficacy of Omegaven for use in the treatment of PNALD in children less than 6 years of age. It has the potential to prevent or delay the need for liver transplantation in children who are exposed to long courses of intravenous nutrition while awaiting intestinal adaptation and growth and may provide a better alternative to our current sole use of ω -6 lipid emulsions associated with PNALD in children unable to achieve full enteral nutrition. It will also demonstrate the essential fatty acid profiles of infants receiving Intralipid (ω -6) as a sole source versus Omegaven (ω -3) as a sole source versus the combination.

PRIMARY OBJECTIVES:

To safely provide Omegaven on a compassionate use basis to Oklahoma children who are dependent on parenteral nutrition and have failed conventional lipid reduction strategies.

To determine the number of these patients who have resolution of their cholestasis (direct bilirubin < 2 mg/dL) within 60 days of initiation of the emulsion.

SECONDARY OBJECTIVE:

[figure not shown]

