Enrolled children will have full growth assessments (weight, length, FOC) and nutritional assessments at every patient encounter (typically this is daily in the hospital and at every GI clinic visit). Any surgical procedures, medications, hospital readmissions, and/or infections directly related to the use of parenteral nutrition will be documented as well as any laboratory, radiology, or pathology data obtained for this purpose while the patient is receiving Omegaven or within 30 days of stopping the lipid.

Table 1: Laboratory Monitoring

	Baseline Day 0	Weekly	Every 2 Weeks	Monthly	After Last Omegaven Dose ¹
While DB \geq 2 mg/dL					
Direct bili	Day -1 to 0	\pm 3 days			Continue weekly until normal
CBC/diff	\pm 3 days		\pm 3 days		Within 7 days
AST/ALT/GGT	\pm 3 days		\pm 3 days		Within 7 days
Triglycerides Lipid panel	\pm 3 days			\pm 3 days	
PT/INR	\pm 3 days			\pm 3 days	Within 14 days
EFAP	Day 0		\pm 3 days		Within 30 \pm 7 days
When DB < 2 mg/dL					
Direct bili			\pm 3 days		
CBC/diff			\pm 3 days		Within 14 days
AST/ALT/GGT			\pm 3 days		Within 14 days
Triglycerides Lipid panel				\pm 3 days	
PT/INR				\pm 3 days	Within 14 days
EFAP			\pm 3 days		Within 30 \pm 7 days

¹If DB remains \geq 2 mg/dL, monitoring will continue until child is off Omegaven for 4 months. When feasible, an EFAP will be obtained approximately 4 weeks after the parenteral nutrition use has ceased.

Dosing Modifications Based on Triglyceride Levels:

- If triglyceride level \leq 250 mg/dL, continue lipids at current dose.
- If triglyceride level $>$ 250 mg/dL, repeat specimen when off lipids for 4 hours. If repeat is \leq 250 mg/dL, continue at current dose. If repeat is $>$ 250 mg/dL, decrease dose by 25% and repeat within 24 hours.
- If triglyceride level $>$ 500, stop lipids immediately with repeat level within 24 hours. Restart lipids at the discretion of the physician.

Other Dosing Modifications:

- For children unable to tolerate Omegaven due to a suspected allergy or toxicity or due to active bleeding believed to be caused or worsened by the lipid emulsion, the infusion may be decreased or stopped at the discretion of the child's medical team with the reason documented.
- The attending physician may choose to decrease or stop lipids at their discretion for any reason if they determine continuing may be detrimental to the patient with

the reason documented.

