- If, for any reason, the supply of Omegaven is interrupted, the infant will receive the standard of care at an equivalent dose until Omegaven is available.

Outpatient Administration:

Children receiving Omegaven at the time of discharge must be seen within the first month in the OU Children's GI Clinic as an outpatient once they are discharged from the hospital. Further outpatient visits should occur no less frequently than every 2 months while on Omegaven. Weight, length, and FOC will be obtained on all children less than 2 years of age; weight and height should be obtained on all children over the age of 2 years. At each outpatient visit, enteral and parenteral nutrition volumes should be recorded. Any surgical procedures, medications, hospital readmissions, and/or infections directly related to the use of parenteral nutrition should be documented as well as any laboratory, radiology, or pathology data obtained for this purpose. Monitoring labs will be performed as per Table 1 as long as the child remains on Omegaven.

Children will be observed in the inpatient setting for a minimum of 48 hours after the initiation of Omegaven. Children will be eligible for Omegaven administration for up to 3 years. Two months before eligibility is lost via this IND, an individual IND will be submitted by the child's physician to the FDA if they expect that the child will need to require ongoing therapy. This can be completed via a new process as of January 2017 at: <http://www.fda.gov/downloads/Drugs/DevelopmentApprovalProcess/HowDrugsareDevelopedandApproved/ApprovalApplications/InvestigationalNewDrugINDApplication/UCM490130.pdf>

Option Care will be the outpatient provider for parenteral nutrition. They are familiar with the procurement and use of Omegaven and have procedures in place for providing training to the families before hospital discharge regarding the administration of parenteral nutrition as well as the reporting of potential adverse events. At the time of discharge, interested parties will be given information regarding potential AEs to be reported and how to directly contact the safety monitor and/or [name]. The family, home health nurse, primary care physician, and GI physician will report any suspected AEs to [name] and/or [name] (safety monitor).

Data Collection:

The following data may be collected for protocol adherence and patient safety analysis.

- Name
- Medical record number
- Date of birth

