- Dates of hospitalization and/or outpatient visits
- Nutritional data (enteral and parenteral)
- Growth data (weight, length/height, FOC)
- Laboratory, microbiology, and pathology data
- Medications, including Ursodiol, phenobarbital, and other enteral lipid products
- Liver and/or intestinal transplant and other pertinent surgical procedures
- Neurodevelopmental testing results
- Mortality
- Adverse event data

Termination and Completion

Termination of a patient's participation will occur if the child develops a serious adverse event definitely caused by the lipid emulsion, if the child is diagnosed after enrollment with a fish allergy or a disorder of lipid metabolism, if the child is unable to tolerate the emulsion, if the child dies, if the child's guardian decides to no longer participate, or if the attending physician feels it is in the child's best interest. In the event this occurs, the date of and reason for termination will be recorded.

Completion of the study occurs when any of the following are met: the child is no longer receiving parenteral nutrition and the direct bilirubin level is <2 mg/dL, the direct bilirubin is ≥ 2 mg/dL and it has been 4 months since the cessation of Omegaven, Omegaven has been used for 3 years, or the child reaches 6 years of age. This does not preclude the patient from receiving the medication, but the patient's current physician will need to apply for a treatment IND and assume monitoring of the patient.

Data and Safety Monitoring Plan

All observed or volunteered adverse events (AE) will be investigated for seriousness and causality within 48 hrs of investigator awareness. AEs will be reported from enrollment through 30 calendar days after the last administration of Omegaven. A serious adverse event (SAE) includes any untoward medical occurrence that results in death, is life-threatening, requires prolongation of existing hospitalization, or results in significant disability.

We will assess adverse events using the following scale (i.e. 3D):

0=No or mild complication

1=Moderate complication with no long-lasting effects

2=Severe, life-threatening, or disabling complication

3=Death

A=UNRELATED or UNLIKELY (clearly not related to the study or the relationship appears to be remote and other factors suggest an alternative etiology exists)

B=POSSIBLE (one or more factors suggest a possible relationship but other etiologies seem equally or more likely)

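### The SAE definition covers a prolonged hospital stay but not a new admission, so an event that brings a child in from home Omegaven can be left out of SAE counts

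*Combined protocol and SAP*

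**What the plan says.** The Data and Safety Monitoring Plan says a serious adverse event includes any untoward occurrence that is fatal, is life-threatening, "requires prolongation of existing hospitalization, or results in significant disability". No other section defines the term. The 0–3 severity scale that follows does not mention hospital admission.

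The protocol also plans for time at home. Under Outpatient Administration, the minimum inpatient observation after starting is 48 hours. "Children receiving Omegaven at the time of discharge must be seen within the first month" at the GI clinic, and "Children will be eligible for Omegaven administration for up to 3 years". Adverse events are collected from enrollment to 30 days after the last dose, so the window covers home use.

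Readmissions are expected. Research Design and Methods states that "hospital readmissions, and/or infections directly related to the use of parenteral nutrition will be documented", and Outpatient Administration repeats this for clinic visits ("hospital readmissions, and/or infections directly related to the use of parenteral nutrition should be documented"). Data Collection lists "Dates of hospitalization and/or outpatient visits" and adverse event data. None of these passages links a readmission to seriousness.

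**The concern.** The hospitalization criterion applies only to a child who is already an inpatient. Many children may spend much of their exposure at home, where there is no existing stay to prolong. Whether an event counts as serious then depends on where the child was when it began, not on the event itself.

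This bears on a primary objective, which is "To safely provide Omegaven on a compassionate use basis to Oklahoma children who are dependent on parenteral nutrition" after conventional lipid reduction has failed. The Abstract adds that "Safety outcomes and the resolution of cholestasis will be monitored and reported to the FDA and IRB". If admissions from home are not classed as serious, SAE figures for home exposure can be too low, and SAE figures for home and inpatient periods are not comparable. Some expedited reports to the FDA also depend on the same classification.

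**Working it through.** The protocol gives no SAE rate, readmission rate or SAE threshold, so there is no figure to reproduce. The check applies the written definition to a case and traces where the result is used.

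**1. Criteria listed.** Death, life-threatening, prolongation of an existing stay, significant disability: 4 in all. Criteria covering a new admission: 0.

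**2. One event, two settings.** IRB Information, item 3, names line sepsis as a risk of parenteral administration. Suppose a line infection is treated and resolves without being fatal, life-threatening or disabling.

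| Criterion | Child in hospital, stay lengthened | Child at home, admitted |
|---|---|---|
| Death | no | no |
| Life-threatening | no | no |
| Prolongs an existing stay | **yes** | no (no stay to prolong) |
| Significant disability | no | no |
| Result under the listed criteria | serious | no criterion met |

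**3. Does another passage close the gap?**
- The severity scale (0–3) refers to moderate, severe, life-threatening or disabling complications and death, not to admission.
- The readmission text in Research Design and Methods and in Outpatient Administration calls for documentation only.
- The reporting paragraph of the Data and Safety Monitoring Plan uses the word *serious* without redefining it.

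None of them does.

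**4. Where the classification is used.** The Data and Safety Monitoring Plan has four expedited triggers:

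| Trigger | Deadline | Turns on the affected classification? |
|---|---|---|
| Unexpected fatal or life-threatening suspected reaction | 7 days | no |
| Serious, unexpected suspected reaction | 15 days | **yes** |
| Findings from other studies that suggest significant human risk | 15 days | no |
| Clinically important rise in the rate of a serious suspected reaction | 15 days | **yes** |

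So 2 of 4 are affected. The last trigger does not require the reaction to be unexpected, so a foreseen event can count toward it if it is a suspected reaction. Whether a particular event would be unexpected, and so fall under the second trigger, cannot be judged from the documents.

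**5. What is not affected.** Every adverse event is still investigated for seriousness and causality within 48 hours of awareness, reviewed quarterly with the safety monitor, and reported to the IRB and FDA at least annually. An admission that is fatal, life-threatening or disabling is an SAE under the existing text.

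**6. Size.** A count of affected events needs the share of children discharged on Omegaven and an admission rate at home. The documents give neither, and the planned maximum of 200 children does not supply them.

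**The case against.** The best case for leaving the text alone has five parts.

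- **The list is open.** The definition says *includes*, and every event gets an individual seriousness judgement. An investigator may therefore class an admission as serious. That is true, but nothing directs it. Because hospitalization appears only as prolongation, a reader could infer that new admissions were left out on purpose, and two assessors could classify the same event differently.
- **FDA requirements may govern.** The reporting timelines are introduced as FDA requirements, so the agency's own meaning of *serious* might override the protocol's list. The documents do not settle this. The loss of a 15-day report is therefore possible, not shown.
- **No SAE output is specified.** The plan defines no SAE endpoint, rate or numeric threshold, and its quarterly and annual channels carry all adverse events. This stands as a limit on the consequence. A quarterly or annual listing is still not a 15-day report, and it does not correct the classification.
- **The affected class is narrow.** For the expedited triggers, the event must also be a suspected reaction, and one of the two triggers requires it to be unexpected. The rate trigger has no baseline or numeric threshold, so the effect of a missing admission on it cannot be measured. These points stand.
- **Widening the definition has a side effect.** Termination and Completion ends participation for an SAE definitely caused by the emulsion, so a broader definition extends the reach of that sentence. This is correct, and the fix has to deal with it.

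**Conclusion.** The concern holds. The only SAE definition omits a new admission in a protocol that plans home treatment for up to 3 years, and no other passage supplies the criterion. Under the literal reading, the same event is serious for an inpatient whose stay is lengthened and non-serious for a child admitted from home.

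The wording leaves 0 of 4 criteria covering a new admission and affects 2 of 4 expedited triggers. The number of events cannot be stated. The conclusion is that admissions from home *can* be left out, not that any have been. It rests on reading the list as written. An investigator who uses the latitude in *includes* would avoid the problem case by case, but not consistently by rule. The 7-day rule is untouched and the events still reach the annual reports. No consequence is claimed for termination under the current text, because other termination grounds are listed. This should be fixed, and the harm is one of classification and possibly of reporting time, not of lost data.

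**What to change.** Three steps:

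1. Reword the hospitalization criterion to *requires inpatient hospitalization or prolongation of existing hospitalization*.
2. Re-review for seriousness the admissions already recorded between enrollment and 30 days after the last Omegaven dose. Identify them from the hospitalization dates and adverse event data named under Data Collection. The readmission records alone may not suffice, because that text can be read as covering only readmissions directly related to parenteral nutrition.
3. The sponsor should reconcile the sentence in Termination and Completion that uses the term serious adverse event with the revised definition. No stopping rule is proposed here.

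The cost is a one-phrase amendment, that reconciliation and a one-time re-review using data types the protocol already lists. SAE counts and the related paperwork would rise by an amount that cannot be estimated from the documents. Counts before and after the change are comparable only if the re-review is done.
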